3.2.2 Physical examinations

Physical examinations (PE) will be performed according to the assessment schedules (see the Schedule of Activities (SoAs) in CSP). Full PE will include assessments of the head, eyes, ears, nose, and throat and the respiratory, cardiovascular, GI, urogenital, musculoskeletal, neurological, dermatological, hematologic/lymphatic, and endocrine systems. Height will be

measured at screening only. Targeted PE are to be utilized by the Investigator on the basis of clinical observations and symptomatology.

As reported in the CSP, any new or aggravated clinically relevant abnormal medical finding at a PE as compared with the baseline assessment will be reported as an AE unless unequivocally related to the disease under study, see Sections 8.3.9 and 8.3.10 of CSP.

Height will be retrieved from parent clinical studies. PE are assessed under “Physical Examination (PE)” eCRF module, the following information are reported:

- Was the PE performed? (y/n)
- What was the PE date?

3.2.3 Vital signs

Vital signs (blood pressure [BP], pulse, temperature, and respiration rate) will be evaluated according to the SoAs. Body weight is also recorded at each visit along with vital signs. Situations in which vital sign results should be reported as AEs are described in Section 8.3.7 for the CSP.

Vital signs are assessed under “Vital Signs Pre-Infusion (VS)”, “Vital Signs During Infusion (VS1)”, and “Vital Signs Post Infusion (VS2)” eCRF modules. The following information are reported in these modules:

- Date of assessment
- Test name (Temperature, Weight, Systolic blood pressure, Diastolic blood pressure, Pulse Rate, Respiratory rate)
- Assessment result and unit

3.2.4 Laboratory safety assessments

Laboratory safety assessments consist of blood and urine samples for determination of clinical chemistry, hematology, TSH, and pregnancy. Situations in which laboratory safety results should be reported as AEs are described in Section 8.3.7 of the CSP.

Laboratory safety assessments are assessed under the following eCRF modules:

- Non-central Laboratory Test Results (LB) - Clinical Chemistry:
 - lab specimen collection date
 - name of the laboratory used
 - test results (including but not limited to: Blood Urea Nitrogen, Bicarbonate, Amylase, Chloride, Lipase, etc.)
- Non-central Laboratory Test Results (LB2) – Hematology

- lab specimen collection date
- name of the laboratory used
- test results (including but not limited to: Hemoglobin, Platelets, Neutrophils Absolute Count, Lymphocytes %/Ratio, Neutrophils %/Ratio, Lymphocytes, Absolute Count, White Blood Cells, etc.)
- Non-central Laboratory Test Results (LB3) - Thyroid Function Tests
 - lab specimen collection date
 - name of the laboratory used
 - test results (T3, Free; T4, Free; Thyroid Stimulating Hormone; Time field for Lab CFs)
- Pregnancy Test (PREG)
 - Sampling date
 - Pregnancy test results (positive/negative)
- Pregnancy Report (PREGREP)
 - Last menstrual period
 - Expected delivery date
 - Subject using hormonal contraception (oral or implant) or an IUD at time of conception (y/n)
 - Previous pregnancies details:
 - Overall number
 - Number of normal deliveries
 - Number of spontaneous miscarriages
 - Number of other previous pregnancies
 - Relevant pregnancy risk factor (smoking, alcohol, etc)
 - Relevant family history

3.2.5 Durvalumab exposure

Exposure (i.e. duration of treatment) will be defined as follows:

Total exposure of study treatment:

Total (or intended) exposure = min (last dose date where dose > 0 [units] + 27 (where 27 is the number of days between dosing – 1), date of death, date of DCO) – first dose date + 1.

Total (or intended) exposure will be expressed in months.

Actual exposure of study treatment

Actual exposure = intended exposure – total duration of dose interruptions, where intended exposure will be calculated as above and a dose interruption is defined as any length of time where the patient has not taken any of the planned daily dose; hence, the total duration of dose interruptions in days is calculated as the cumulated lengths between the interruption dose date and the resuming dose day + 1.

Actual exposure and total duration of dose interruptions will be expressed in months. The actual exposure calculation will make no adjustment for any dose reductions that may have occurred.

3.2.6 Relative Dose Intensity (RDI)

Relative dose intensity (RDI) is the percentage of the actual dose delivered relative to the intended dose through to treatment discontinuation. RDI will be defined as follows:

RDI = 100% * d/D, where:

- d is the actual cumulative dose delivered up to the actual last day of dosing. Actual dose (in mg) is reported in “Exposure - durvalumab (EX)” eCRF form as “**Study drug dose per administration**” Actual cumulative dose will be calculated by summing all doses for each day, across all treatment cycles.
- D is the intended cumulative dose up to and including the actual last day of dosing. D is the total dose that would be delivered, if there were no modification to dose or schedule. Intended dose (in mg) is reported in “Exposure - durvalumab (EX)” eCRF form as “**Planned study drug dose per administration**”.

The total number of planned doses will be calculated as the following: round ((last dosed date – first dosed date +28)/28)

When accounting for the calculation of intended cumulative dose 3 days will be added to the date of last dose to reflect the protocol allowed window for dosing.

4 OTHER ASSESSMENTS

In addition to primary and secondary variables that will be collected under this study, other key information will be collected using either directly into Electronic Data Capture (EDC) system or transferred from clinical parent studies (Table 2).

Table 2. Parent study assessments

Study variables	Data source

 • Parent study protocol number, study e-CODE 	EDC entry

 • Vital signs (weight, temperature, blood pressure, pulse rate, respiratory rate) 	

 • Date and last dose of durvalumab and durvalumab combination treatment administration 	

 • Ongoing safety events at the end of parent study 	

Study variables	Data source

 • Ongoing concomitant medications at the end of the parent study • Subsequent anticancer therapy 	

 • Patient identification or linkage key, including connection to the Interactive Voice/Web Response System (IxRS) and EDC and transfer of old enrolment code (E-code) • Demographics: date of birth 	New IxRS system

 • Date of randomization from parent study (for randomized parent studies) • Date of first administration of durvalumab and durvalumab combination treatment (for non-randomized parent studies). • Height 	Transfer of data from clinical parent study (SDTM data)

 • Contact information: (patient, caregiver, physician) as allowed by regulation for each country 	Patient contact module

In addition to parent study assessments, the following data will be collected and described:

- Disposition of Subjects, assessed at study termination, under “disposition (DS)” eCRF module. The following information will be collected:
 - Discontinuation date
 - Subject’s status at discontinuation: Death, Lost to follow-up, Screen failure, Withdrawal by subject, Withdrawal by parent/guardian, Development of study-specific withdrawal criteria (to be specified), Other (to be specified), Adverse Event, and Pregnancy
- Patient demographic and Other Baseline Characteristics assessed at baseline visit:
 - Age
 - Sex
 - Race
 - Ethnicity
 - Country
- **[Only for Cohort 1 and Cohort 2]** Exposure to durvalumab assessed under “Exposure - durvalumab (EX)” eCRF module. The following information will be collected:
 - Start date and time
 - End date and times
 - Dose per administration

- Dose units
- Action taken (dose not changed, drug interrupted, Drug permanently discontinued)
- Main reason for action taken (AE, other (to be specified))
- Treatment cycle delayed (y/n)
- Reason for treatment cycle delayed (Delayed hematological recovery, Adverse event, Disease symptoms, Logistic, Subject decision, Lab abnormality not reported as an AE, Other (to be specified))
- Concomitant and other treatments assessed under “Prior and Concomitant Medications (CM)” eCRF module. The following information will be collected:
 - Medication verbatim name
 - AE number for which medication taken
 - Medical history condition(s) number for which medication taken
 - Medication route of administration
 - Total daily dose
 - Dose unit
 - Medication dosing frequency
 - Treatment start date
 - Treatment stop date
 - Ongoing treatment (y/n)
 - Indication
- Concomitant Procedures assessed under “Concomitant Procedures (CONPRO)” eCRF module:
 - Procedure text
 - Procedure start date
 - Procedure reason
- Current and Concurrent cancer therapy assessed under “Current Cancer Therapy (CAPRX1)” and “Cancer Therapy - Post withdrawal of IP (CAPRX2)” eCRF modules respectively. The following information will be collected:
 - Cancer therapy agent name
 - Route of administration
 - Number of cycles
 - Therapy class (Immunotherapy, Hormonal Therapy, Cytotoxic chemotherapy, Systemic Therapy, Targeted Therapy, Antiangiogenic Therapy, Taxane chemotherapy, Radiopharmaceuticals, Platinum Chemotherapy, PARP Inhibitor, Biologic therapy, Experimental therapy, Other)

- Start and stop dates
- Best response (CR, PR, SD, Progression, Non-evaluable, Not applicable)
- Treatment status (line of therapy, adjuvant/non-adjuvant, palliative, maintenance, Definitive, Not applicable)
- Radiotherapy:
 - Timing against withdrawal of IP: previous, current, post
 - Radiotherapy site or region
 - Radiotherapy start and stop dates
 - Dose per fraction (Gy)
 - Number of fraction doses (total)
 - Treatment status (Adjuvant, Neo-adjuvant, Palliative, Definitive, Not applicable)

5 ANALYSIS METHODS

5.1 General principles

The below mentioned general principles will be followed throughout the study:

- Descriptive statistics will be used for all variables, as appropriate. Continuous variables will be summarized by the number of observations, mean, standard deviation(Sd), median, upper and lower quartiles minimum, and maximum. Categorical variables will be summarized by frequency counts and percentages for each category.
- Unless otherwise stated, percentages will be calculated out of the population total for the corresponding analysis set.
- For continuous data, the mean and median will be rounded to 1 additional decimal place compared to the original data. The Sd will be rounded to 2 additional decimal places compared to the original data. Minimum and maximum will be displayed with the same accuracy as the original data.
- For categorical data, percentages will be rounded to 1 decimal place.
- There are no statistical methods that will be employed to test a specific hypothesis.
- SAS® version 9.4 or later will be used for all analyses.

For efficacy endpoints (only considered for Cohort 2), the last observed measurement prior to retreatment will be considered the baseline measurement.

For safety endpoints (where all cohorts are considered) the last observation before the first dose of study treatment will be considered the baseline measurement. For assessments on the day of first dose/randomization date where time is not captured, a nominal pre-dose indicator will serve as sufficient evidence that the assessment occurred prior to first dose. Assessments

on the day of the first dose where neither time nor a nominal pre-dose indicator are captured will be considered prior to the first dose if such procedures are required by the protocol to be conducted before the first dose.

In all summaries change from baseline variables will be calculated as the post-treatment value minus the value at baseline. The percentage change from baseline will be calculated as $(\text{post-baseline value} - \text{baseline value}) / \text{baseline value} \times 100$.

5.2 Analysis methods

5.2.1 Overall survival (OS)

A listing of the OS data will be provided in the FAS, for each cohort. This listing will contain the following information: patient identifier, cohort, date of randomization, date of first dose, survival status (death or no death), date of death or date last known to be alive; days from randomization to death with a flag indicating if the value is censored, cause of death, autopsy performed (yes/no), and death related to disease under investigation (yes/no).

Note: In addition to listings, survival and tumor efficacy data may be combined with the parent study data for an integrated analysis on a “as needed” basis. The Kaplan Meier (KM) approach, Log-Rank test, Cox Proportional Hazards model, etc., will be used if OS analyses are requested for a parent study.

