9.3.2 Efficacy analyses

One secondary objective is to assess the efficacy of durvalumab in terms of ORR and DOR for retreated patients. The analysis set for ORR and DOR will be based on the patients who undergo retreatment with durvalumab in Cohort 2. Data will be summarized by tumor type if there is sufficient sample size in each tumor type. ORR will be estimated with a 95% CI using the exact probability method. The median DOR and its 95% CI will be estimated using the Kaplan-Meier method. ORR and DOR will be assessed in the response evaluable analysis set. If there are not sufficient counts of retreated patients to conduct the efficacy analysis, then only listings will be provided. Further detail will be provided in the SAP.

A listing of OS data will be provided for full analysis set.

In addition, survival and tumor efficacy data in this study may be combined with the parent study data for integrated analysis. In the integrated analysis, OS will be described using the Kaplan-Meier method.

Efficacy of durvalumab will be assessed in terms of ORR, DOR, and OS as defined in Section 9.3.3.

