1 STUDY DETAILS

1.1 Study objectives

The study objectives will be assessed among 3 cohorts defined according to treatment status, these cohorts are described in Section 1.2.

The objectives of this study as well as corresponding endpoints are as follows:

Table 1. Study objectives and endpoints

Primary objective	Endpoints/Variables:
To monitor long term safety of durvalumab (all cohorts)	
 • All SAEs • Non-serious AEs that lead to dose modification, drug discontinuation, or withdrawal from the study • All Grade 3 and Grade 4 AEs • Grade 2 AEs that affect vital organs (eg, heart, liver) • Immune-mediated AEs • Laboratory findings qualifying as an SAE/AE (endpoints defined above) up until 90 days after the last dose of durvalumab in all patients
Secondary Objectives:	Endpoints/Variables:
To assess the efficacy of durvalumab in terms of ORR and DOR in patients who undergo retreatment with durvalumab (Cohort 2 only)	
ORR: Number (%) of patients with a confirmed response of CR or PR.
 
DOR: Time from first documented CR or PR to time of first documented disease progression or death in the absence of disease progression

To assess the OS of patients (all cohorts)	
OS: Time from date of randomization/date of first dose ^a in the parent clinical study until the date of death by any cause

AE adverse event; CR complete response; DOR duration of response; ORR Objective response rate; OS overall survival; PR partial response; SAE serious adverse event.

^a For randomized parent studies, the randomization date will be used in the calculation of OS. For single-arm parent studies, the date of first dose will be used in the calculation of OS.

[figure not shown]

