2 ANALYSIS SETS

2.1 Definition of analysis sets

2.1.1 Full Analysis Set (FAS)

The FAS will include all patients enrolled in the study, regardless of the treatment received. OS analysis will be performed on the FAS. In addition, demographic and patient characteristics will be summarized amongst the FAS population.

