3.1.3 Overall survival (OS)

OS will be assessed in the FAS.

OS is defined as the time from the date of randomization/date of first dose in the parent clinical study until death due to any cause. For randomized parent studies, the randomization date will be used in the calculation of OS. For single-arm parent studies (durvalumab monotherapy) and combination parent studies, the date of first dose (durvalumab or combination treatment) will be used in the calculation of OS.

Any patient not known to have died at the time of analysis will be censored based on the last recorded date on which the patient was known to be alive (Date subject confirmed to be alive (SUR_DAT), recorded within the SURVIVE module of the eCRF).

Patient contact calls to determine survival will be made within 7 days following the date of DCO for the OS analysis, and if patients are confirmed to be alive or if the death date is after the DCO date these patients will be censored at the date of DCO. The status of ongoing, withdrawn (from the study) and “lost to follow-up” patients at the time of the final OS analysis should be obtained by the site personnel by checking the patient’s notes, hospital records, contacting the patient’s general practitioner and checking publicly available death registries. In the event that the patient has actively withdrawn consent to the processing of their personal data, the vital status of the patient can be obtained by site personnel from publicly available resources where it is possible to do so under applicable local laws.

Note that when a survival sweep is performed the SURVIVE module should be completed for every patient.

Note, for any OS analysis performed prior to the final OS analysis, in the absence of survival calls being made, it may be necessary to use all relevant case report forms (CRF) fields to determine the last recorded date on which the patient was known to be alive for those patients still on treatment (since the SURVIVE module is only completed for patients off treatment if a survival sweep is not performed). The last date for each individual patient is defined as the latest among the following dates recorded on the CRFs:

- AE start and stop dates
- Admission and discharge dates of hospitalization

- Study treatment date
- End of treatment date
- Laboratory test dates
- Date of vital signs
- Disease assessment dates on RECIST CRF
- Start and stop dates of alternative anticancer treatment

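### Overall survival is a secondary objective in all cohorts, but WAVE commits only to a patient listing, with no estimate and no WAVE enrollment date

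*SAP*

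**What the plan says.** SAP 1.1 and Protocol Section 3 (Table 4) make OS in all cohorts a secondary objective. SAP 2.1.1 names the population: "OS analysis will be performed on the FAS". That set is everyone enrolled in WAVE. SAP 3.1.3 fixes the clock: "OS is defined as the time from the date of randomization/date of first dose in the parent clinical study until death due to any cause". It then gives rules for censoring, survival sweeps and partial death dates.

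The output is the same in both documents. SAP 5.2.1 says "A listing of the OS data will be provided in the FAS, for each cohort", and Protocol 9.3.2 says "A listing of OS data will be provided for full analysis set". After patient identifier and cohort, the columns are "date of randomization, date of first dose, survival status (death or no death), date of death or date last known to be alive", then "days from randomization to death with a flag indicating if the value is censored", and details of the death. The WAVE enrollment date is not among them.

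Both sections add that survival data may be combined with parent-study data. Protocol 9.3.2 names Kaplan-Meier for that analysis; SAP 5.2.1 adds the log-rank test and Cox model, to be used if a parent study asks for OS analyses.

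**The concern.** There are two linked problems. First, a listing of up to 600 patients is not an assessment of survival. The same SAP commits to an exact confidence interval for response rate (5.2.2) and to Kaplan-Meier medians with intervals for duration of response and time to response (5.2.3, 5.2.4), all in the retreated part of Cohort 2, which may be too small to analyze. OS, which covers everyone, gets no estimate.

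Second, the listing invites a mistake. Each patient carries a survival time that starts in the parent study, yet is in the data only because he or she lived long enough to consent to WAVE. A reader who draws a curve from those times counts months in which death could not have been observed. The date needed to remove those months is not listed.

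**Working it through.** **Plan's own figure.** There is none to reproduce: the plan has no OS event target, power statement or hypothesis test, and 600 is a ceiling set by availability (Protocol 9.1). The check sets the definitions side by side, then sizes the error under assumptions.

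**Definitions.**
- Time origin: parent randomization or first dose (SAP 3.1.3).
- Population: enrolled in WAVE (SAP 2.1.1), with written consent (Protocol 5.1), so alive at enrollment.
- Entry time L: from parent origin to WAVE enrollment; not in the listing.
- Neither document mentions delayed entry, left truncation or a landmark.

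**Why a naive curve is too high.** At time t the correct risk set is the patients with L < t who are still under observation. The naive risk set also includes patients who enroll after t. The deaths are the same and the denominator is larger, so each estimated hazard is too small. If nobody enrolls before month 12, naive 12-month survival is 1.00 by construction.

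**Size, on assumed inputs.** Exponential survival with median m; L uniform between l and h; only patients alive at L kept; WAVE follow-up uniform on 12 to 39 months. The upper limit reflects Q3 2019 to Q4 2022, which is 36 to 42 months. The documents give neither m nor L; their nearest guide is parent treatment of up to 12 months in multiple studies (Protocol 2.2.2).

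The target for patients entering from month l onward is S(t)/S(l) = 2^(−(t−l)/m), with median l + m. For m = 24 and l = 12, S(24)/S(12) = 2^(−12/24) = 0.707 and the median is 36.

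| m | Entry (months) | Naive median | l + m | Excess | Naive S(24) | S(24)/S(l) |
|---|---|---|---|---|---|---|
| 12 | 6–24 | 26.2 | 18 | 8.2 | 0.568 | 0.354 |
| 12 | 12–48 | 38.0 | 24 | 14.0 | 0.826 | 0.500 |
| 18 | 6–24 | 32.5 | 24 | 8.5 | 0.693 | 0.500 |
| 18 | 12–36 | 41.1 | 30 | 11.1 | 0.870 | 0.630 |
| 24 | 12–36 | 47.3 | 36 | 11.3 | 0.905 | 0.707 |
| 36 | 6–24 | 50.8 | 42 | 8.8 | 0.837 | 0.707 |
| 36 | 12–48 | 65.5 | 48 | 17.5 | 0.955 | 0.794 |

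Over all 12 combinations run (four medians, three entry ranges), the excess in the median is 8.2 to 17.5 months, and in 24-month survival 0.13 (0.837 − 0.707) to 0.33 (0.826 − 0.500). Against unconditional survival from parent start the gap is wider: 14 to 30 months, and 0.21 to 0.58. Letting follow-up start at 0 instead of 12 months moves the two 18-month rows only to about 33 and 42 months.

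**Does delayed entry repair it?** Here it does, to within about 0.01 of S(t)/S(l), because entry time was simulated independently of prognosis. It fails when that is untrue. Suppose half the patients have median 36 months and enter at 12 to 36 months, and half have median 9 and enter at 6 to 15. The true median given survival to month 6 is about 25.2 months; delayed entry gives 15.5. Kaplan-Meier from WAVE enrollment gives about 19 months, against a true post-enrollment median of about 19.

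**The case against.** The strongest reply is that listing-only is deliberate. The synopsis, Protocol 9.3.2 and SAP 5.2.1 agree on it, the primary aim is safety, no hypothesis is tested, and the parent-study origin makes sense if the data are meant to feed parent-study analyses. An integrated analysis that keeps all parent-arm patients, including those who died before WAVE, would not have this bias.

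Much of that stands. A reader might infer that SAP 2.1.1 and 3.1.3 contradict 5.2.1. They do not: 2.1.1 names the analysis set, and the listing needs the censoring rules because it carries a censoring flag. A reader might also infer that the plan reports an inflated survival estimate. It does not, since no planned WAVE output draws the curve. Nor are the data beyond repair: the enrollment date must exist, because Safety Analysis Set membership depends on it (SAP 2.1.3) and it sets the Cohort 3 baseline (Protocol 9.3.3.1).

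The reply does not remove the gap. The integrated analysis is optional, and neither document says it will keep the early deaths. Having no hypothesis test is no reason to omit an estimate; duration of response is estimated without one. The listed first-dose date is no substitute for enrollment: SAP 3.1.3 points to the parent dose, and Cohort 3 and non-retreated Cohort 2 patients receive no WAVE dose.

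**Conclusion.** The point holds as a gap in the analysis plan, not as a bias in a planned result. WAVE has a secondary survival objective and no committed estimate to answer it, and its listing lacks the date needed to use the listed times correctly. That a naive curve errs upward follows from the design. The size is illustrative: it rests on exponential survival and on assumed medians and entry gaps.

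A related defect supports revising the section: the listing counts days from randomization, while SAP 3.1.3 starts OS at first dose for single-arm and combination parent studies. The listed time therefore does not match the definition there, and has no start date where a parent study was not randomized.

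**What to change.** In SAP 5.2.1:

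1. Add the WAVE enrollment date to the listing, and list survival time from the origin that applies to each patient.
2. Add descriptive Kaplan-Meier survival by cohort, measured from WAVE enrollment, with median, yearly rates and 95% confidence intervals. Split by parent indication where numbers allow.
3. If survival from parent start is also shown, use delayed entry at WAVE enrollment. Label it conditional on survival to the earliest entry time, and state that it assumes entry time is independent of prognosis. That is doubtful here, because Cohorts 1 and 2 are selected on benefit or absence of progression.
4. State that any integrated OS analysis keeps all patients of the parent arm, including those who died before WAVE.

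The cost is SAP wording, one enrollment-date column, a relabeled time column, and one table and figure per cohort. Pooled curves mix tumor types, regimens and times since parent start, so they must be read descriptively.
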